## 8.0 Study design

The Bariatric Surgery Registry is a population based, observational and epidemiological quality improvement study of persons with obesity who undergo bariatric surgery. Non-probability sampling is necessary as the Registry aims to capture the entire population.

Surgeons and/or gastroenterologists who are known to perform bariatric procedures are invited to participate in the Registry. Whilst their participation is voluntary, they are asked to sign a participation agreement stating that they have read the protocol and will maintain the responsibility for their patients’ data. All surgeons and gastroenterologists are provided with flyers and a poster for the recruitment of Registry participants using the opt out approach. They are also given **The BSR-i User Manual for Surgeons and Staff** and when requested, paper data forms for submitting their patient and operation information.

Those submitting data directly on the Registry’s web-based interface, the BSR-i, will be given a user ID and temporary password. **The BSR-i User Manual for Surgeons and Staff** contains an authorisation form to record anyone who enters information regarding patients on the behalf of surgeons or gastroenterologists. Data collectors in public hospitals who enter data on the BSR-i are provided with their own account and are able to submit data for each of those hospitals’ surgeons and gastroenterologists that participate in the Registry.

Private and public hospitals in Australia and New Zealand that care for persons who have or had bariatric surgery will be contacted to participate in the Registry. Ethics approval and site or locality approvals are to be sought for each hospital. A Memorandum of Understanding between Monash University and each hospital/hospital group representative should be executed prior to the commencement data collection at the hospital(s). Once these steps have been taken and all approvals has been granted for the hospital’s or hospital group’s participation, Registry staff will contact the person at the hospital responsible for discharge coding. A template will be provided to the coder along with access to a secure file transfer platform to send the coding reports to the Registry.

Principal investigators with credentials for the hospital site will ensure the project is conducted in accordance with the National Statement on Ethical Conduct in Research 2007 (2018) and assist with the ethical and research requirements for the site.

Demographic and operation information for each patient undergoing a bariatric surgical procedure is submitted to the Registry following surgery. Data related to patient outcomes during the 90-day period after the surgery is collected for all participants and annually for primary participants.

The Bariatric Surgery Registry conforms to the Operating Principles and Technical Standards for Australian Clinical Quality Registries (2008) as set out by the ACSQHC. The Registry is expected to be ongoing and data will be retained indefinitely.

## 8.1 Participant eligibility

Anyone who undergoes bariatric surgery as treatment for obesity in Australia or New Zealand is eligible for inclusion for the study (non-probability sampling). The minimum age for eligibility is set at 2 years and a maximum age of 95 years.

[figure not shown]
The study population may include:

- children or young persons;
- persons with a cognitive impairment;
- people highly dependent on medical care;
- persons who cannot speak English; and/or
- persons who identify as Aboriginal, Torres Strait Islander peoples, Māori or Pacific Islands peoples.

Pregnant females are not considered for bariatric surgery and are therefore excluded from the study.

**Figure 1** illustrates the overall recruitment process for the participation of hospitals, surgeons, gastroenterologists and bariatric patients in the research.

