## 4.0 Aims

As a clinical quality registry, the purpose of the Bariatric Surgery Registry is to gather and analyse data in order to monitor and enhance the quality of care received by obese persons undergoing bariatric surgery.

The aims of the Bariatric Surgery Registry are:

- to record the immediate safety of bariatric surgery in Australia and New Zealand;
- to longitudinally study the safety and efficacy of bariatric surgery in Australia and New Zealand assessing procedures, devices, complications and adverse events;
- to track key health changes including weight loss/BMI and diabetes management following bariatric surgery in Australia and New Zealand;
- to report accurate population level data to shape health practices and policy;
- to be a basis for further research into bariatric surgery as a safe and effective treatment for obesity; and
- to allow better analysis of the economic benefits of bariatric surgery as a treatment for obesity related illness.

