### 4. The effect of bariatric surgery on long term weight loss

Data collected:

- participant weight at baseline
- participant height
- participant weight on annual basis (following a primary bariatric procedure)

Interval: 12 months to 10 years after a primary bariatric procedure

Demonstrates: the sustainability of weight loss in the long term

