### 8.4.3 Data elements

Data elements are defined in the Registry's data dictionary and governed by the Steering Committee, with any changes managed through a data element variation process.

The data elements collected include:

- **Patient data elements:**

*Patient Identifiers:*

- full name;
- address;
- date of birth;
- UR number/hospital (and IHI numbers when available); and
- email address (if supplied by patient)

- **Patient demographic information:**

- Medicare number (Australia only)
- Department of Veterans Affairs (DVA) number;
- NHI number (New Zealand only);
- phone numbers;
- gender; and
- indigenous status (Australia)/ethnicity (New Zealand)

- **Operation data elements:**

*Clinical details:*

- start weight (for primary participants only);
- day-of-surgery (DOS) weight;
- height;
- diabetes status and treatment; and
- concurrent renal and liver transplant

*Procedural information:*

- surgeon name;
- procedure date;
- procedure type;
- surgical approach used (open, laparoscopic, robotic)
- primary/ revision;
- planned or unplanned revision status;
- reason for revision;
- bariatric procedure prior to revision;
- if the procedure was abandoned;
- reason for abandoning procedure;
- length of hospital stay; and
- mortality status including date of death and whether the death was likely to be related to the bariatric procedure

*Device or Staple details:*

- type;
- brand;
- model;
- port fixation method; and
- buttress

- **Follow-up data elements**

*Elements for Perioperative (up to 90 days post-surgery) Data:*

- date participant had a post-operative review
- occurrence of unplanned return to theatre and reason/ complication occurrence of unplanned admission to intensive care and reason/ complication;
- occurrence of unplanned re-admission to hospital and reason/ complication;
- prolonged hospital stay and reason/ complication; and,

- mortality status including date of death and whether the death was likely to be related to the bariatric procedure

*Elements for Subsequent Clinical Data of Primary Participants (collected annually for ten years):*

- weight;
- diabetes status and treatment;
- re-operation and reason; and
- mortality status including date of death and whether the death was likely to be related to the bariatric procedure

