### 9.1.1 Ethical considerations for children or young persons

As bariatric surgery is known to be performed on children and young people, persons under 18 years old are expected to be recruited to participate in the Registry. The collection of their data is essential to reliably report the appropriateness, safety and effectiveness of bariatric surgery as a treatment for obesity in young people.

Children and young persons will not be directly involved in the research as observational data is collected from surgeons, gastroenterologists and hospitals. Their participation in the Registry has a low risk to their safety, emotional and psychological security and well-being.

Written consent will be required for the participation of any minor in the Registry, following the process as set out in section 8.3.2. When a minor participant reaches 18 years, consent for participation will be re-negotiated for those whose participation was consented by a parent or guardian. This allows the individual to decide for his/her self whether or not to continue their involvement with the study. Refer to section 8.3.2.1.

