### 13.1 Publicly available reports

As required by the 2008 ACSQHC Operating Principles, the Registry produces regular publicly available reports. **Annual reports** comprehensively review the data held on the Registry's database, analysing the safety and quality of bariatric surgical procedures and the effect on participants' clinical outcomes (diabetes management and total and excess weight loss maintained following surgery). These aggregate reports are available on the Bariatric Surgery Registry website and are sent directly to contributing surgeons, gastroenterologists, hospital executives, hospital group executives, ethics committees, state and federal health departments, medical device manufacturers, third party private insurers and other professional organisations with a vested interest in the outcomes of bariatric surgery. **A semi-annual brief update** is also made available by the same channels.

Annual reports are published as at June 30 each year and are released in the September of the same year. The semi-annual update is published as at 31 December each year and is released in the following March.

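### Minors are eligible from age 2, but no repeat height is listed, so follow-up BMI in participants who are still growing can only use the operation height and is overstated

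*Protocol*

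**What the plan says.** **Who is included.** Section 8.1 sets the age range: "The minimum age for eligibility is set at 2 years", with an upper limit of 95. Minors are not just a theoretical possibility, since section 9.1.1 says "persons under 18 years old are expected to be recruited to participate in the Registry" and section 8.3.2 gives them their own written consent pathway.

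**What is collected, and when.** In section 8.4.3, height stands among the clinical details of the operation, beside start weight and day-of-surgery weight. The later block is headed "Elements for Subsequent Clinical Data of Primary Participants (collected annually for ten years" and has four items: weight, diabetes, re-operation and mortality. Height is not one of them. Quality indicator 4 in section 6.0 has the same pattern. It asks for baseline weight and "participant weight on annual basis (following a primary bariatric procedure", and lists height once with no timing, over an interval of 12 months to 10 years. In Table 5, the electronic medical record row brings in weight, diabetes information and further operations, but no height. Section 8.4.2.2 asks for height only to complete an operation record found through hospital coding.

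**What is promised.** Section 4.0 includes the aim "to track key health changes including weight loss/BMI and diabetes management following bariatric surgery". Section 13.1 says the annual reports cover "total and excess weight loss maintained following surgery". Section 9.1.1 calls minors' data essential in order to "reliably report the appropriateness, safety and effectiveness of bariatric surgery as a treatment for obesity in young people".

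**The concern.** In adults one height is enough, because it does not change materially over follow-up. In a child or adolescent it does. BMI after surgery needs the height at that time, and the Protocol lists only the height at operation. The data set therefore does not support the BMI aim for participants who are still growing.

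The error runs one way: an outdated, shorter height makes follow-up BMI too high and the benefit of surgery too small. It falls on results in young people, which section 9.1.1 gives as the reason for including them. It is also a data-collection gap: an analysis can drop or approximate the affected values, but it cannot recover a height that was not measured while the participant was growing.

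**Working it through.** The Protocol states no figure on this point, so there is none to reproduce. All heights, weights and the reference BMI of 25 below are assumptions for illustration.

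**1. BMI.** Let h0 be the height at operation, h1 the current height and w1 the current weight.

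- Correct follow-up BMI = w1 / h1²
- BMI on operation height = w1 / h0²
- Ratio = (h1 / h0)², which does not depend on weight

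| Growth | Ratio | Overstatement |
|---|---|---|
| none | 1.000 | 0% |
| 2% | 1.02² = 1.040 | 4.0% |
| 160 to 165 cm | (165/160)² = 1.063 | 6.3% |
| 5% | 1.05² = 1.103 | 10.3% |
| 150 to 165 cm | (165/150)² = 1.210 | 21.0% |

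**2. One participant.** Assume 100 kg at 150 cm, later 80 kg at 165 cm.

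- Baseline BMI: 100 / 1.50² = 44.4
- Follow-up BMI, current height: 80 / 1.65² = 29.4
- Follow-up BMI, operation height: 80 / 1.50² = 35.6
- BMI reduction, current height: (44.4 − 29.4) / 44.4 = 34%
- BMI reduction, operation height: (44.4 − 35.6) / 44.4 = 20%

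**3. Excess weight loss.** The answer depends on the definition, which the Protocol does not print. Assume 120 kg at 1.65 m, later 95 kg at 1.70 m, with reference weight 25 × height².

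- Reference weight at operation: 25 × 1.65² = 68.1 kg, so excess = 120 − 68.1 = 51.9 kg
- *Definition A, excess fixed at baseline:* (120 − 95) / 51.9 = 48.1%. Only the operation height is needed.
- *Definition B, reference weight follows current height:* reference = 25 × 1.70² = 72.25 kg; remaining excess = 95 − 72.25 = 22.75 kg; loss = (51.94 − 22.75) / 51.94 = 56.2%

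Under B, lacking the later height understates the result by about 8 percentage points. With growth to 1.75 m, B gives (51.94 − 18.44) / 51.94 = 64.5% against 48.1%. Under A there is no computational error.

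**4. Total weight loss.** (w0 − w1) / w0, where w0 is the baseline weight, contains no height, so its formula is unaffected. It makes no allowance for weight gained through growth, but a height field would not change that.

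**5. Reach.** In an all-age mean BMI, the error is the share of growing minors multiplied by their mean individual error. The Protocol does not give that share. Section 3.1 puts the annual volume at about 27,000 procedures, so if minors are few the aggregate hardly moves.

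**The case against.** The strongest reply is that the Protocol prints no BMI or excess-weight-loss formula and does not say which height is used. Section 8.4.3 introduces its list as what the data elements include and refers to a data dictionary that is not shown; a repeat height could be defined there. Indicator 4 attaches no timing to height at all. This stands as a limit on certainty. It does not remove the point, because section 8.4.3 itemises the annual data and leaves height out, and indicator 4 marks weight, but not height, as annual.

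A reader might infer that the registry's published BMI and excess-weight-loss results are wrong. The documents do not support that. Excess weight loss can be defined entirely on the operation height. Reports are aggregate, no separate paediatric BMI report is promised, adults and minors who have finished growing are unaffected, and the number of growing minors is unknown. A lower age limit of 2 suits a registry that aims to capture everyone; it does not show that very young children are operated on in number. The mortality, adverse-event, re-operation and diabetes indicators need no height.

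It is also fair to say that an analysis plan can leave out minors' visits without a current height. That prevents a misleading figure but leaves no BMI result for those visits. Age- and sex-standardised BMI and separate reporting of minors are ordinary analysis-plan matters, and their absence here is no fault.

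A revision operation would create a new operation record, possibly with a new height, but that is not scheduled follow-up.

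**Conclusion.** The point holds as a data-collection gap of limited reach. Followed as written, the Protocol gives no current height for participants who grow during follow-up, although it aims to track their BMI. Their follow-up BMI is overstated by (h1/h0)²: about 6% for 160 to 165 cm and 21% for 150 to 165 cm. The formula is exact; the heights are assumed.

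For excess weight loss the conclusion is conditional: it is understated if the reference weight is meant to reflect current height, and not otherwise. The effect is confined to growing minors and is probably small in all-age summaries. The verdict rests on the printed element lists being complete for height; a repeat height in the data dictionary would resolve it.

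**What to change.** Add to the annual elements in section 8.4.3, and to indicator 4 in section 6.0, a conditional item: height, for participants under 18 at surgery, until growth is complete. If the data dictionary already holds such an item, list it in both places. State that minors' visits without a current height are left out of BMI summaries and of any excess-weight-loss summary whose reference weight depends on current height. Age- and sex-standardised BMI and separate reporting of minors can be left to the analysis plan.

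The cost is one extra field for what is probably a small group, with matching changes to the data dictionary and, where that route is used, to the medical-record extract. Section 8.4.3 already restricts start weight to primary participants and provides a process for varying data elements, so the change fits the existing structure. The main weakness is quality: when follow-up is by telephone under section 8.4.2.3, height would be reported by the participant or parent rather than measured, so the source of the value should be recorded.

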**Figure 1. Recruitment for the Bariatric Surgery Registry**

## 8.2 Consent

The opt out approach to participation is used in for those individuals who are considered able to provide independent informed consent, due to the scale and significance of the Registry. In New Zealand, the age at which an individual can provide independent informed consent is 16 years. However, the Registry will use the age of 18 years in Australia, as the age when an individual can provide independent consent varies amongst its states and territories. This will ensure consistency amongst Australian participants. Written informed consent will be used for those considered to be 'minors' (those under the age of 16 in New Zealand and under the age of 18 in Australia).

The Bariatric Surgery Registry adheres to the Guidelines Approved under Sec 95A of the *Privacy Act 1988* (2014) and the National Statement on Ethical Conduct in Human Research 2007 (Updated 2018), in its rationale for the use of the opt out approach.

Although opt out will be most commonly used, a participant's capacity for consent will need to be considered according to the National Statement. The responsibility for determining capacity of consent will be with the clinician. The concerns and needs of specific groups of participants are discussed in sections **9.1-1.5**.

In accordance with the State and Federal privacy legislation of Australia and New Zealand, the National Statement for Ethical Conduct in Research (AU), and New Zealand's Ethical Guidelines, approval for using the opt out approach will be sought from an ethics committee nominated by the hospital and the Southern Health and Disability Ethics Committee in New Zealand.

## 8.3 Participant recruitment

Eligible participants are recruited (see **Figure 2**) when:

- a surgeon, gastroenterologist or public hospital data collector submits patient details into the BSR-*i* or with an operation form; or
- the Registry receives International Classification of Disease 10-Australia Modified (ICD-10-AM) coding reports (or similar hospital discharge reports) from contributing hospitals or hospital groups (discussed further in section **8.4.2.2**).

### 8.3.1 Recruitment of eligible participants aged 16 or over (NZ) or 18 or over (AU)

Participants aged 16 or over (NZ) or 18 or over (AU) are recruited using the opt out approach according to the requirements set out in Sections 2.3.6-2.3.12 of the National Statement on Ethical Conduct in Research 2007 (2018). Prospective participants must be told that their identifiable health information will be provided to the Bariatric Surgery Registry for medical research that is in the public interest. This is done by surgeons, gastroenterologists and/or public hospital clinic staff who are to provide their bariatric patients with a Registry information flyer and display a poster which states that their practice or clinic participates in the Bariatric Surgery Registry.

In plain English language, both the poster and flyer advise prospective participants that the Registry will contact them after their surgery. The flyer explains:

- that the Bariatric Surgery Registry follows the progress of everyone who has a bariatric procedure in Australia and New Zealand;
- what information is collected by the Registry;
- the voluntary nature of their participation; and
- that they can inform their surgeon or gastroenterologist of their intention for non-participation.

After the surgery is performed, surgeons, gastroenterologists, public hospital data collectors, nurses and hospital information services provide data to the Registry related to the prospective participant's details and their bariatric procedure/s. Data is provided via paper forms or by direct entry on the web

interface, the BSR-*i*. Upon receipt of this data, the Registry posts potential participants a Participant Fact Sheet (PFS), Bariatric Surgery Registry Fact Sheet and a flyer (as a reminder of the one they received prior to surgery). The PFS explains the purpose of the Bariatric Surgery Registry and what their involvement entails. It also advises that their participation is voluntary and how to opt out if they do not want to be involved. General contact information is listed along with details about making a complaint to the relevant ethics committee and a free call number (1 800 in Australia or 0 800 in New Zealand) is also provided.

These steps ensure that prospective participants are fully informed that their sensitive health data will be transmitted to a third party, the Bariatric Surgery Registry at Monash University or Auckland UniServices.

Bariatric patients have three options for participation:

1. **Full participation** – Their data is included on the Registry, and Registry staff may contact the participant for follow-up information. If the bariatric patient wishes to participate, no further action is required by them upon receiving the Participant Fact Sheet. Patient information is systematically included on the Registry after 14 days from when the PFS was posted.
2. **Partial opt out** – Their data is included on the Registry but Registry staff will not contact the participant for follow-up information. The bariatric patient is required to phone the free call 1 800 number (AU) or 0 800 number (NZ) to state their decision to partially opt out.
3. **Opt out** - No clinical data is retained on the Registry. Bariatric patients who choose to opt out are required to phone the free call 1 800 number (AU) or 0 800 number (NZ) listed on the PFS and state their decision not to participate. Participants can choose to opt out at any time.

The Registry will keep the patients' name, date of birth, treating hospital & UR Number/NHI and treating surgeon in a secure "Do Not Contact" file to ensure the patients will not be contacted in the future about that procedure. All information related to their bariatric procedure will be removed from the database and destroyed if in paper form.

Participants who opt out or withdraw will be, upon request, sent a letter confirming their withdrawal or, if they have left a voice message. The decision to opt out is recorded per bariatric procedure. Should the Registry be notified in the future that the patient has undergone a further revision procedure, they will go through the opt out approach again allowing them to re-consider whether they wish to be involved with that subsequent operation.

[figure not shown]
Amongst the participants who choose to opt out are those who request that their details not be kept in any file. These individuals are advised that removing all of their details may result in their being sent another PFS if information related to their procedure is added again. The individual will be advised to contact their surgeon's/gastroenterologist's rooms to have this decision recorded so that any request by the Registry for information related to that procedure will not be submitted.

A secure file is kept of individuals who opt out and this file is strictly accessible to Registry staff only. All health information for those who opt out is deleted and/or destroyed, if in paper form, in accordance with the National Statement for Ethical Conduct in Human Research 2007 (2018). The information kept in the secure file is only that which is needed to ensure the individual will not be contacted again about their procedure, including their name, date of birth, name of the treating surgeon or gastroenterologist and hospital. When individuals contact the Registry to opt out, they will be asked for their verbal consent for this information being kept for this purpose. This retained information validates that the procedure was submitted, ensuring and verifying that surgeons are not selectively enrolling participants. Furthermore, the file allows for accurate reporting of participant opt-out and withdrawal rates, preventing the Registry from reporting a false opt out rate.

If a PFS is returned in the mail, Registry staff will attempt to validate the address used. If a corrected and current address cannot be obtained, all information related to the patient will be deleted and securely destroyed, if in paper form, as the opt out approach is not able to be completed.

**Figure 2** illustrates the typical participant recruitment process as well as recruitment and data verification using the information collected from the hospital discharge reports.

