## 9 Ethical considerations

The Bariatric Surgery Registry was established for the purposes of health research and is considered to be in the public's interest and follows the specific recommendations by the Georganas Inquiry into Obesity in 2009, the Australian Commission on Safety and Quality in Healthcare, and the Health Technology Review Report.

To function as a clinical quality registry, the Bariatric Surgery Registry collects, stores, and uses identifiable, personal and sensitive health information about bariatric patients for research into the quality, safety and effectiveness of bariatric surgery as treatment for obesity. In order to collect longitudinal outcomes of those who underwent bariatric surgery, identifiable information is necessary so that hospitals, surgeons, gastroenterologists and their staff can link back to participants' medical records and provide information on participants' health status following their procedures.

Ordinarily, consent is sought from individuals whose health information is being collected. All quality and safety registries require near total capture of potentially eligible participants to ensure reliable reporting of outcomes. If participation in a quality and safety registry is less than 90%, there is significant risk of bias and underreporting of adverse outcomes. International experience suggests that obtaining prior consent can cause participation rates to drop to around 60%, potentially rendering data unreliable. Obtaining consent, therefore, for a clinical quality registry would 'prejudice [its] scientific value', justifying the use the opt out approach when considering New Zealand's Ethical Guidelines for Observational Studies.

Further, based on the anticipated numbers of participants expected to be recruited for the study, obtaining direct consent would be difficult. Based on the current data, it is estimated that least 27,000 bariatric patients per year will be eligible for recruitment across Australia and New Zealand. As such, the scale and significance of the Bariatric Surgery Registry indicates that an opt out approach to participation, rather than informed consent, is necessary.

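### Records destroyed after a returned fact sheet are not counted, so participation read from the opt-out percentage is overstated by about the deleted share

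*Protocol*

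**What the plan says.** Section 8.3.1 treats two groups differently.

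- **People who opt out.** Their health information is destroyed, but a few identifying items stay in a secure file. The section gives reasons for keeping them. They show that the procedure was submitted, they guard against clinicians choosing whom to enrol, and "the file allows for accurate reporting of participant opt-out and withdrawal rates, preventing the Registry from reporting a false opt out rate".
- **People whose fact sheet is returned.** First, "Registry staff will attempt to validate the address used". Then, if no current address is found, "all information related to the patient will be deleted and securely destroyed". The reason given is "as the opt out approach is not able to be completed". No file, log or count is described for this group.

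Three other places bear on the point.

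- Section 8.3 (Participant recruitment) treats an eligible patient as recruited when a clinician or data collector submits details, or when a hospital coding report arrives.
- Section 13 (Reporting) has the opt-out percentage reported as the indicator of how far recruited patients take part.
- Sections 8.4.2.2 and 8.4.4 check completeness against hospital coding reports, which cover participating clinicians only and reveal procedures that the Registry does not hold.

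**The concern.** A patient deleted for returned mail has been submitted, and so counts as recruited under Section 8.3, but does not take part. The patient has not opted out either, so the opt-out percentage is silent about them. The two safeguards that Section 8.3.1 values for opt-outs, proof of submission and a check on selective enrolment, do not reach this group because nothing about them is kept.

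Two things are at stake. The participation figure that Section 13 draws from the opt-out percentage will look better than the truth. And a clinician who did submit the case can no longer be shown to have done so. If the procedure later appears in a coding report as not held, it will look like the clinician's omission and may set off a fresh data request and a repeat mailing. Section 8.3.1 itself warns of repeat mailing for opt-outs who ask that nothing be kept.

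**Working it through.** The protocol gives no figure for returned mail, so there is no stated result to reproduce. The calculation below shows only how the error scales.

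**Inputs**
- N = 27,000 eligible a year (Sections 3.1 and 9). The percentages below do not depend on N.
- o = opt-out share of all submitted. Section 10 says it has stayed below 4%; 4% is used as the upper bound.
- r = share of submitted records deleted after returned mail. Not in the protocol; 1%, 2% and 5% are assumed for illustration.

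**Formulas**
- Deleted records leave nothing to count, so they drop out of the denominator. The observed opt-out rate is oN / (N − rN) = o / (1 − r).
- Participation read from it: 1 − o / (1 − r).
- True participation among those submitted, with no other losses: 1 − o − r.
- Overstatement: the difference, which simplifies to r × [1 − o / (1 − r)]. This is slightly less than r.

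**Results for o = 4% (1,080 opt-outs a year)**

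| r (assumed) | Deleted a year | Observed opt-out rate | Participation read from it | True participation | Overstatement |
|---|---|---|---|---|---|
| 1% | 270 | 1,080 / 26,730 = 4.04% | 95.96% | 95% | 0.96 points |
| 2% | 540 | 1,080 / 26,460 = 4.08% | 95.92% | 94% | 1.92 points |
| 5% | 1,350 | 1,080 / 25,650 = 4.21% | 95.79% | 91% | 4.79 points |

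With o = 2%, the overstatement at r = 1%, 2% and 5% is 0.98, 1.96 and 4.89 points. The result therefore depends on r and hardly at all on o.

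The opt-out rate moves by at most 0.21 points over this range, and upward. The weakness lies in using that rate as the measure of participation.

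**The case against.** The strongest reply is that deletion is a deliberate consent safeguard. The waiver in Section 8.3.3.1 covers data held until two weeks after posting, and a patient who could not be informed should not be kept. That stands, and nothing here asks for the record to be kept. An aggregate count holds no individual's health information.

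A second reply is that an opt-out rate among patients who could be informed is a legitimate statistic. That also stands. The difficulty is only that Section 13 reads it as participation among those recruited.

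A reader might infer more than the protocol supports:

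- *That the Registry ignores the phone and email details it holds.* Section 8.3.1 does not say how an address is validated, so staff may telephone the patient or the surgeon's rooms. Section 8.4.3 lists email only where supplied, and the coding extract in Table 5 lists neither phone nor email. What can be said is that a corrected address is the only stated way to avoid deletion.
- *That capture rates are misstated.* At participating sites a deleted case can reappear in a coding report and lower measured capture. The loss is liable to be attributed to the wrong cause, but it is not shown to be hidden there.
- *That people who "request that their details not be kept in any file" go uncounted.* The protocol places them among the opt-outs and does not say they are left out of the total. It does not describe how they are counted either.
- *That the 95% capture aim in Section 3.1 is missed, or the 90% mark in Section 9 ("If participation in a quality and safety registry is less than 90%, there is significant risk of bias and underreporting of adverse outcomes") is breached or nearly so.* Both depend on r, which is unknown, and the 95% aim is set against all procedures performed, not those submitted.
- *That the deleted patients have worse outcomes.* It is plausible that they differ, but the protocol has no data on this.

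**Conclusion.** The point holds as a reporting defect. Followed as written, the protocol destroys a submitted record without trace and then measures participation by a percentage that cannot see it. Participation is overstated by slightly less than the deleted share: about 1 point if 1% are deleted and about 5 points if 5% are. The direction follows from the text. The size rests on an assumed share, which may be smaller in practice because only mail still unresolved after address validation counts. Bias in the safety or effectiveness results is not demonstrated. The remedy is cheap, and without it the size of the loss cannot be established afterwards.

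**What to change.** In Section 8.3.1, before a returned-mail record is destroyed, add one to a non-identifying tally by site, surgeon, period and primary or revision procedure (where known). Do the same for opt-outs who want no details kept, so that they stay in the opt-out total.

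In Section 13:
- report the returned-mail tally beside the opt-out percentage;
- compute participation as included / (included + opted out + deleted for returned mail).

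In Section 8.4.4, use the tally when reconciling coding-report gaps, so that a deleted case is not put down to the clinician. Cells by surgeon may be small, so public reports should give totals only.

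One sentence in Section 8.3.1 should say how addresses are validated. Optionally, and subject to ethics approval, where a phone number or email is held it could be used to obtain a current address or deliver the fact sheet before deletion.

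The cost is a wording change, a counter and a small amount of staff time. Only the optional contact step changes the approved opt-out process.
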